3.4.3. Sub-study analysis populations

The primary set of subjects for exploratory efficacy analyses is the *Safety set of subjects* who had at least one sample collected in the TrypSkin sub-study.

The secondary set of subjects for exploratory efficacy analyses is the set of all seropositive subjects who were positive for the presence of trypanosome by at least one method in skin, drawn blood and/or DBS at baseline.

3.4.4. Determining actual treatment received

Treatment misallocation was identified during the study through PK analysis where samples from a few participants expected to be randomized in the acoziborole arm showed no concentration of acoziborole. Therefore, it was decided to analyze 1 timepoint of PK samples for all participants (i.e. D5 sample and if D5 sample is not available then M1 timepoint) for detection/non-detection of acoziborole in blood purposes. Since this is primarily a safety study, it is conservative to consider participants to have taken active treatment as long as there is detection of any amount of acoziborole in blood; thus, any safety events in those patients would be attributed to acoziborole given its long half-life. Since study drug is only taken once, participants with no acoziborole detected by PK after that dose will be assumed to have taken placebo. The PK concentration data will then be used to determine the actual treatment received which will be merged with other Study Data Tabulation Model (SDTM) datasets at unblinding.

4. Trial Population

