#### 8.3.4. Pharmacokinetic analyses

PK analyses will be performed at Day 5 (steady state) and Month 1 (in accordance with acceptable time window of Table 3).

Whole blood (5 x 10  $\mu$ L) will be deposited on filter paper using the DBS technique and shipped to the reference laboratory for analyses.

For the first 192 subjects administered with the study drug, and who have a valid ECG and a PK sample at D5, PK samples will be analysed to assess correlation between  $\Delta QTc$  measurements (ECG assessment) and acoziborole DBS concentrations at D5.

The rest of PK samples will be stored and could be analysed in case of unexpected AE, if the samples are still within the stability deadline.

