3.4.1. Subject Disposition populations

The Screened set includes all subjects who were screened and provided informed consent by signing the ICF.

Intent-to-Treat set (ITT) includes subjects who signed the informed consent and were considered eligible by the investigator and randomized into the study, i.e., randomized to receive acoziborole or placebo. Data should be reported based on the treatment to which subjects were randomly assigned (i.e., regardless of the actual treatment received).

The Treated set includes all randomized subjects who received three tablets of IP (placebo or acoziborole).

PK analysis set includes all randomized subjects who received at least one tablet of IP (placebo or acoziborole) and for whom at least one blood sample for pharmacokinetics is available.

Modified ITT (mITT) is composed of all ITT subjects who received at least one tablet of IP (placebo or acoziborole). Data should be reported based on the treatment to which subjects were randomly assigned (i.e., regardless of the actual treatment received).

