3.4.2. Main study analysis populations

Safety set of subjects (SS) is composed of all subjects in the PK analysis set. This analysis population will be the primary set of subjects for the main study analyzed per the actual treatment received. Actual treatment received will be determined by detection/non-detection of acoziborole in blood through PK analysis. Additional primary analysis will be performed using the safety set of subjects excluding subjects with treatment misallocation.

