5.1. Primary Objective Analysis

The assessment of the safety of a single dose of acoziborole compared to placebo during a follow up period of 4 months will be conducted using excess rate (ER) of occurrence of any TEAE over the first 4 months in the acoziborole group compared to placebo. The numerator of the occurrence rate will be the number of subjects with at least one TEAE and the denominator will be the number of subjects in the Safety Set. In addition, a sensitivity analysis will be performed on safety set population excluding subjects with treatment misallocation. The ER is the occurrence rate of any TEAE in the acoziborole group minus the occurrence rate in the placebo group. The 95% confidence interval (CI) of the excess rate will be calculated using Wilson score interval (which provides average coverage very close to 95% in all cases⁹). The excess rate (ER) of occurrence of any TEAE will be transformed to the number of subjects needed to treat (NNT) to observe one more subject with a TEAE in the acoziborole group compared to placebo (NNT = 1 / ER).

The analysis will be performed on the total SS population and by age groups (defined as adolescents aged 15-17 years and adults aged \geq 18 years), gender, TEAE severity category and period of occurrence. Four categorizations of TEAEs per severity will be derived as 1) Serious AEs regardless of the relationship to drug, 2) severe and related to drug TEAEs and 3) mild and/or moderate regardless of relationship to drug, and 4) severe but not related to drug. TEAEs period of occurrence will be categorized as: 1) Occurrence during the hospitalization period and 2) Occurrence after the hospitalization period (from EoH to month 4). The same event for the same subject can occur at both periods (i.e., the event is still present at the second period). However, for the analysis the AE start date will be used to identify AEs in each period. The denominator of occurrence rates will be the number of subjects receiving at least one tablet of IP for the first period and the number of subjects attending the 4-month visit or having reported a TEAE during the second period.

The occurrence rate analysis will be performed on a safety set. MedDRA preferred terms of TEAE with occurrence rates ≥1% in one treatment group will be compared between treatment groups on the excess rates and NNT for any TEAE, by TEAE severity to assess whether the more severe

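### One unconfirmed non-detected PK sample moves an acoziborole-randomised subject, with any TEAEs, to placebo in the primary analysis, and no TEAE analysis is planned as randomised

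*SAP*

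**What the plan says.** SAP 3.4.2 defines the Safety Set and states: "This analysis population will be the primary set of subjects for the main study analyzed per the actual treatment received". The arm comes from PK alone: "Actual treatment received will be determined by detection/non-detection of acoziborole in blood through PK analysis".

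SAP 3.4.4 gives the reason. During the study, a few participants expected to be on acoziborole had no measurable drug, so "it was decided to analyze 1 timepoint of PK samples for all participants". The sample used is the "D5 sample and if D5 sample is not available then M1 timepoint", so Month 1 replaces a missing Day 5 sample and never confirms a negative one. Any detected amount counts as active treatment, which the SAP justifies as conservative for a safety study. For the opposite result, "participants with no acoziborole detected by PK after that dose will be assumed to have taken placebo", on the ground that the drug is taken only once. The section mentions no second sample, repeat assay, kit reconciliation, quantification limit or stability limit.

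SAP 5.1 plans one alternative: "a sensitivity analysis will be performed on safety set population excluding subjects with treatment misallocation". SAP 3.4.1 also defines ITT and mITT sets, for which "Data should be reported based on the treatment to which subjects were randomly assigned". However, the TEAE and AE comparisons in SAP 5.1 and 5.2.1 are specified on the Safety Set. SAP 4.2 uses ITT for demographics. Protocol 10.2 had defined the Safety Set itself as an mITT set with no PK requirement.

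**The concern.** The two halves of the rule do not err in the same direction. Counting any detection as active can only add exposure, and the events that go with it, to acoziborole. Counting non-detection as placebo takes a subject's events out of the active arm and adds them to an arm one third its size. If the subject did take acoziborole, both effects lower the excess rate, which is the primary outcome. The SAP's argument about conservatism does not cover this half.

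A non-detect can arise without a wrong kit: a swapped or failed spot, a degraded sample, or a dose lost almost entirely by vomiting. Vomiting is the awkward case, because it may itself be a TEAE and would then be counted on placebo. The exclusion analysis relies on the same PK classification, so it deletes such a subject's events and cannot restore them to acoziborole. The results most exposed are uncommon and serious events, and uncommon TEAEs are what the sample size was built around.

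**Working it through.** **Inputs from the documents.** Arms of 900 and 300 (SAP 2.4.1). Planning rates of 2% v 1% for an AE of interest (SAP 2.4.3). Tmax about 72 h and half-life about 400 h (SAP 1.1). PK samples at 96 h and 30 days (Protocol Table 3). Wilson-based 95% limits (SAP 5.1), here combined by Newcombe's method for a difference.

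**Assumptions.** The number of subjects moved, k, and all event rates other than 2% v 1%. The SAP gives no count beyond a few.

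**1. The plan's own figure.** P(at least one event) = 1 − (1 − p)^n. For p = 0.2% and n = 900 this is 83.50%, as stated. With 1 to 20 subjects removed (n = 899 to 880) it is 83.47% to 82.83%. Detection probability is barely affected; the issue is where events are counted.

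**2. AE of interest, 18/900 v 3/300.** Let e of the k moved subjects have the event.
- Moved: ER = (18 − e)/(900 − k) − (3 + e)/(300 + k)
- Excluded: ER = (18 − e)/(900 − k) − 3/300
- One moved event costs about 1/900 + 1/300 = 0.11 + 0.33 = 0.44 points.

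As randomised, ER = +1.00% (−1.03 to 2.32).

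| k | Moved, all with event | Excluded, all with event | Moved, none with event |
|---|---|---|---|
| 1 | 17/899 − 4/301 = +0.56% (−1.59 to 1.94) | +0.89% (−1.13 to 2.19) | +1.01% |
| 3 | 15/897 − 6/303 = −0.31% (−2.67 to 1.20) | +0.67% (−1.34 to 1.93) | +1.02% |
| 5 | 13/895 − 8/305 = −1.17% (−3.71 to 0.47) | +0.45% (−1.54 to 1.66) | +1.03% |

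In the worst case three moved subjects reverse the sign of the estimate. Every interval shown includes zero.

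**3. Serious events (assumed 9/900 v 1/300).** As randomised: 1.00% − 0.33% = +0.67%. With two events moved: 7/898 − 3/302 = 0.78% − 0.99% = −0.21%. If five subjects were moved independently of events, the chance that two or more had a 1% event is 1 − 0.99^5 − 5(0.01)(0.99^4) = 0.1%. A link between event and non-detection, such as vomiting, would raise it.

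**4. Any TEAE (rates assumed).**
- 40% in both arms, five subjects with TEAEs moved: 355/895 − 125/305 = 39.7% − 41.0% = −1.3 points.
- True excess of 5 points, placebo rates 20%, 40% and 60%, five subjects with TEAEs moved: the excess falls to 3.27, 3.71 and 4.15 points.
- Same, but the moved subjects have the acoziborole arm's average rate: 5 × 300/305 = 4.92 points.

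**5. Is Month 1 informative?** Assuming simple exponential decline, the level at 96 h is 0.5^((96 − 72)/400) = 96% of peak. The level at 720 h relative to 96 h is 0.5^((720 − 96)/400) = 34%. A retained dose should be detectable near its peak on Day 5, and at about a third of that level at Month 1. The second sample can therefore help tell a swapped or failed Day 5 spot from true non-exposure.

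**The case against.** The strongest reply is that misallocation was actually found. If placebo was given, counting the subject on placebo is right for safety, and an as-randomised analysis would put unexposed subjects in the acoziborole arm and dilute the excess. That stands: the as-randomised result is a companion to the as-treated one, not a replacement.

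A false non-detect after a retained dose is also unlikely on the SAP's own PK figures. Since any amount counts as active, only near-total loss by vomiting would matter, and vomiting within an hour is already tabulated and listed (SAP 4.5). The exclusion analysis removes contamination of placebo and keeps the sign positive in the worst cases shown for one to five subjects. Deaths, serious TEAEs and TEAEs of grade 3 or higher are listed individually (SAP 5.1). All of this stands and limits the size of the problem.

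A reader might infer that expired spots were used. Protocol 8.3.4 allows stored samples to be analysed "if the samples are still within the stability deadline", SAP 3.4.4 does not repeat that condition, and Protocol 9.2 refers to 1.5 years of study conduct. The documents do not support the inference. The Protocol states the deadline for samples analysed after an unexpected AE, no stability period is given, and SAP 5.2.6 defers PK analysis to separate reporting, where assay and stability limits may be set.

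None of this supplies confirmation of a non-detect or an as-randomised TEAE result.

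**Conclusion.** The point holds as a gap in the plan and should be fixed before PK-based treatment is merged at unblinding. Arm membership in the primary analysis rests on one sample, and the direction that can hide harm is neither covered by the SAP's argument nor checked by an analysis that returns the events to acoziborole.

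The size is conditional. It is up to about 0.44 points per moved event at 900/300, and only if the subject really took acoziborole and had the event. With average event rates it is small: 5.00 to 4.92 points for five subjects. The vulnerable results are uncommon or serious events.

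It would be tempting to read the rule as biased toward safety in general, or the primary result as unreliable. The documents do not support that: where placebo was truly given the rule is correct, and no misclassified subject is shown. The number moved and the event rates, other than the planning 2% v 1%, are assumptions.

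**What to change.** 1. **SAP 5.1.** Report the primary excess rate also on the mITT set as randomised, as a sensitivity analysis beside the PK-based result. Show the counts in each set, because mITT also includes treated subjects without a PK sample, who are outside the Safety Set.
2. **SAP 3.4.4.** Leave the rule that any detection means active unchanged. For acoziborole-randomised non-detects only, confirm with the other stored PK sample where there is one and with kit accountability records, and state whether the assayed sample was within its stability period. The stability statement is needed separately: a Month 1 spot is only about 26 days younger than the Day 5 spot, so it guards against swaps and failed spots more than against long storage. Flag unconfirmed cases and show the result with them counted in each arm in turn.
3. **Listing.** List every reassigned subject with randomised arm, PK result and all TEAEs, including vomiting within one hour of dosing.

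The cost is SAP wording, one extra table, one listing and a few assays of spots already stored.

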4.1. Trial Subject Disposition

All subjects who provide informed consent will be accounted for in this study. Subject disposition and withdrawals will be presented for the screening analysis set. The total number of screened subjects, reasons for screening failure, number randomized, and reasons not randomized will be summarized and tabulated by site. A Consolidated Standards of Reporting Trials (CONSORT) flow diagram will be used to summarize the number of subjects who were screened, eligible/ineligible, randomized, lost to follow up, discontinued and those completed study.

The status of eligible and randomized subjects at trial end will be tabulated by treatment group according to study follow up status. Time from randomization to withdrawal/lost to follow-up will be presented graphically using the Kaplan-Meier estimator. A summary of the analysis population sets by treatment group and subjects excluded from analysis population will be provided. The data listing for subjects excluded from the population analysis sets will be provided including the reasons for exclusion. A summary of protocol deviations (PDs) will be provided including minor/major classification and PDs categorizations. The PD categorization and classification will be determined before the database lock and unblinding. PD individual data listing will also be provided.

4.2. Baseline Subject Characteristics

Subject demographic characteristics to be summarized will include gender, age in years by treatment group and overall, for the ITT set. The subject demographic will also be summarized for the Safety Set (SS). Subject demographics will be summarized using descriptive statistics (N, mean, standard deviation, median, 25th/75th percentiles, minimum, and maximum) for age variable, and number and percentages of subjects for gender and categorized age (adolescent 15-17 years and adults ≥18 years) variables. Subject demographic data listings will be provided.

4.3. Medical history

Medical history data will be coded using the Medical Dictionary for Regulatory Activities (MedDRA) version 21.0 or higher. System organ classes (SOC) and preferred terms (PT) will be added to the clinical database. The numbers and percentages of subjects in the safety set with a medical history will be summarized by SOC and PT and presented overall and by treatment group. Subjects will appear in the table only once per SOC and PT. The table will be sorted alphabetically by SOC and then by descending frequency of PT in the "Overall" column. A listing of all medical history data will be provided.

4.4. Previous and concomitant medications

Previous medications, defined as any medications taken prior to study treatment intake, and concomitant medications, defined as any medications other than study drugs that are taken between first study treatment intake and the end-of-study visit, will be coded using the WHO Drug Dictionary – March 2019 version or higher. Medication could be both previous and concomitant, if started before first study drug intake and continuing after first study drug intake. The Anatomical Therapeutic Chemical (ATC) preferred names and codes will be added to the clinical database. The numbers and percentages of subjects in the safety set with a previous medication and those with a concomitant medication will be summarized by ATC level 2 and ATC level 3 and presented overall and by treatment for the safety set. Subjects will appear in the summaries only once. The summaries will be sorted alphabetically by ATC level 2 and then by decreasing frequency of ATC levels 3 in the "Overall" column. A listing of all previous and concomitant medications will be provided.

4.5. Treatment Compliance

Information regarding the number of subjects who have taken all three tablets during the single dose of study treatment and the number of subjects who vomit in the hour following the administration will be presented descriptively and data listing provided for the safety set (SS). The treatment compliance will also be summarized for the exploratory TrypSkin sub study.

5. Analysis

5.1. Primary Objective Analysis

The assessment of the safety of a single dose of acoziborole compared to placebo during a follow up period of 4 months will be conducted using excess rate (ER) of occurrence of any TEAE over the first 4 months in the acoziborole group compared to placebo. The numerator of the occurrence rate will be the number of subjects with at least one TEAE and the denominator will be the number of subjects in the Safety Set. In addition, a sensitivity analysis will be performed on safety set population excluding subjects with treatment misallocation. The ER is the occurrence rate of any TEAE in the acoziborole group minus the occurrence rate in the placebo group. The 95% confidence interval (CI) of the excess rate will be calculated using Wilson score interval (which provides average coverage very close to 95% in all cases⁹). The excess rate (ER) of occurrence of any TEAE will be transformed to the number of subjects needed to treat (NNT) to observe one more subject with a TEAE in the acoziborole group compared to placebo (NNT = 1 / ER).

The analysis will be performed on the total SS population and by age groups (defined as adolescents aged 15-17 years and adults aged \geq 18 years), gender, TEAE severity category and period of occurrence. Four categorizations of TEAEs per severity will be derived as 1) Serious AEs regardless of the relationship to drug, 2) severe and related to drug TEAEs and 3) mild and/or moderate regardless of relationship to drug, and 4) severe but not related to drug. TEAEs period of occurrence will be categorized as: 1) Occurrence during the hospitalization period and 2) Occurrence after the hospitalization period (from EoH to month 4). The same event for the same subject can occur at both periods (i.e., the event is still present at the second period). However, for the analysis the AE start date will be used to identify AEs in each period. The denominator of occurrence rates will be the number of subjects receiving at least one tablet of IP for the first period and the number of subjects attending the 4-month visit or having reported a TEAE during the second period.

The occurrence rate analysis will be performed on a safety set. MedDRA preferred terms of TEAE with occurrence rates ≥1% in one treatment group will be compared between treatment groups on the excess rates and NNT for any TEAE, by TEAE severity to assess whether the more severe

events are not "diluted" in non-severe events and by period of occurrence to assess whether the late events are not "diluted" in all events.

A Cochran Mantel-Haenszel test stratified on the site of investigation will be used to compare the occurrence rate of both treatment groups. The same test will be applied to the common TEAE (>1% in any group) based on preferred terms. Generalizability of the treatment effect will be assessed using a test of homogeneity of the odds ratio (OR) across study centers. If the number of randomized subjects in each site reaches 100, then each site will be a stratum. If one or several sites had fewer than 100 subjects, then the smallest sites will be pooled together to obtain strata of at least 100 subjects. If the test of homogeneity is not significant (i.e., p-value ≥ 0.05), the combined odds ratio will be estimated as well as the 95% CI. If the hypothesis of homogeneity is rejected (i.e., p-value<0.05), then the odds ratio per site will be provided.

Time course treatment effect will be analyzed using a log rank test stratified by site and treatment group on the time to occurrence of TEAEs, considering the attrition rate of followed subjects. A loss to follow-up or a withdrawal will be censored at the time of the last attended visit. Kaplan Meier estimates of the proportion of subjects without any TEAE will be presented graphically to assess the time course of the response including results from log rank test.

The rate of occurrence of AEs will be analyzed by the true positive status (subjects with parasites detected during the follow up period) in either treatment or placebo groups.

The rate of conversion to parasite positive and the rate of return to seronegative over 4 months will be analyzed descriptively using frequency and proportion by treatment group.

There is a multiplicity of testing issue, and an inflation of type one error that cannot be discarded. However, no adjustments of type one error are planned because the goal of the trial is to detect any potential safety signals instead of confirming and investigating a safety concern.

The listings for the TEAEs resulting in death, Serious TEAEs and TEAEs of grade 3 or higher will be provided.

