## 1.4. Safety in humans

As of 19 January 2021, 310 subjects, including 102 healthy male subjects of sub-Saharan African origin in DNDiOXA001, 208 patients with HAT in DNDi-OXA-02-HAT study and 6 healthy Caucasian male subjects in DNDi-OXA-03-HAT were exposed to single doses of acoziborole from 20 to 1200 mg.

In study DNDiOXA001, single doses of acoziborole from 20 mg to 1200 mg were well tolerated overall in healthy subjects of sub-Saharan African origins. The most frequently reported adverse events (AEs) after acoziborole administration were gastrointestinal disorders, abnormalities on investigations (CPK increases, transaminase increases and thyroid hormone fluctuations) and central nervous system-related disorders (mainly headache). The frequency and severity were similar for subjects receiving active and placebo in this study. In addition, some of the abnormalities could be explained by the long follow-up period, which increased the probability of detecting non-drug-related fluctuations and use of activated charcoal. One serious adverse event (SAE) judged possibly related to acoziborole and therefore, a serious adverse reaction (SAR) of transient, mild "*asymptomatic hyperthyroidism*" (preferred term [PT]: hyperthyroidism; assessed as related to acoziborole), was reported after administration of a single dose of acoziborole 240 mg, on the basis of variations of thyroid function tests. It resolved spontaneously within 24 days of onset. This event triggered additional monitoring of thyroid function in subsequent cohorts and studies, however no thyroid-related safety signal has since been observed.

In study DNDi-OXA-02-HAT, 260 patients with HAT were included, among whom, 208 patients were exposed to a single dose of acoziborole 960 mg. A total of 27 treatment-emergent SAEs were reported in 21 patients exposed to acoziborole, all of which were assessed as not related to acoziborole. The most frequently reported SAEs were in the system organ class (SOC) Infections and infestations (n=10; 9 patients) or were related to neuropsychiatric disorders (n=9; 8 patients), including one fatal SAE in the SOC Nervous system disorders ("progressive peripheral ascending polyneuropathy"). Six cases of foetal exposure to acoziborole during pregnancies were reported. The outcomes were as follows:

- Pregnancies: all pregnancies had a normal duration with no complication;
- Deliveries:
  - 5 new-borns were in good general health at birth;

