## 8.5.6. Grading of adverse event severity

For each serious and non-serious AEs, the investigator is required to assess the severity of each AE.

The severity is a clinical determination of the intensity of a specific event.

The severity of the AE will be graded according to the National Cancer Institute's Common Terminology Criteria for Adverse Events (NCI CTCAE, version 4.03) as a guide in the grading of the severity of AEs.

In case of an AE is not described in the CTCAE version 4.03, the investigator will use the terminology MILD, MODERATE, or SEVERE to describe the maximum severity of the AE. This information will be entered in the AE page of the CRF. For purposes of consistency, these severity grades are defined as follows:

- MILD: The subject is aware of the event or symptom, but the event or symptom is easily tolerated (e.g. no reduction in daily activities is required).
- MODERATE: The subject experiences sufficient discomfort to interfere with or reduces his or her usual level of activity.
- SEVERE: Significant impairment of functioning: the subject is unable to carry out usual activities and/or the subject's life is at risk from the event.
- LIFE-THREATENING: The subject is at significant risk of life; it does not refer to an event which hypothetically might have caused death if it were more severe (life-threatening consequences, urgent intervention required).
- DEATH: Death related to an event.

When the intensity of an AE changes over time, each change in intensity will be recorded in the source documents until the event resolves. However, only one AE and the maximum intensity will be recorded in the CRF for each separate event. If the AE resolves but then recurs, each will be recorded as a separate AE, with the appropriate start and stop times.

There is a distinction between severity and seriousness: a severe AE is not necessarily a serious event.

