#### 10.7. Safety analysis

#### **10.7.1.** Primary endpoint analysis

Adverse events will be coded using the Medical Dictionary for Regulatory Activities (MedDRA) SOC and PT. Occurrence rates of each TEAE (≥1%), by MedDRA PT, will be compared.

The primary endpoint for this study is the occurrence of TEAEs from administration of study drug to 4 months post-treatment. It is a binary endpoint (presence or absence of any TEAE).

The primary outcome measure is the ER of TEAEs over the first 4 months post-treatment in the acoziborole group compared with placebo. The occurrence rate will be the number of subjects with at least one TEAE as the numerator and the number of subjects who receive at

least one tablet of study medication (the SS) as the denominator. Loss of subjects to follow-up and withdrawal for a reason unrelated to safety or tolerance will not be considered as AEs.

The ER of occurrence of any TEAE will be transformed to the number of subjects needed to treat (NNT) to observe one more subject with a TEAE in the acoziborole group compared with placebo (NNT=1/ER).

The Cochran-Mantel-Haenszel test, stratified by study centre, will be used to compare the occurrence rate of TEAEs between treatment groups. The same test will be applied to the primary endpoint and each component of the composite endpoint (common TEAEs based on PTs).

Generalisability of the treatment effect will be assessed using a test of homogeneity of the odds ratio (OR) across study centres. If the number of randomised subjects in each study centre reaches 100, each study centre will be considered as a stratum. If one or several study centres has fewer than 100 subjects, the smallest study centres will be pooled together to obtain strata of at least 100 subjects. If the test of homogeneity is not significant, the common OR and the 95% CI will be estimated. If the hypothesis of homogeneity is rejected, the OR per study centre will be provided.

Treatment-emergent AEs will be categorised by severity.

All statistics will be provided to ensure that the most pertinent events (serious and severe) are not "lost" amongst non-serious and non-severe events.

Treatment-emergent AEs will also be categorised by period of occurrence during the study. Two successive periods of time will be considered:

- Occurrence during the hospitalisation period
- Occurrence or prevalence after the hospitalisation period (from discharge to Month 4).

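### SAP 5.1 splits severe TEAEs by investigator causality and specifies no excess rate, interval, NNT or test for all severe TEAEs together

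*SAP*

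**What the plan says.** Protocol 10.7.1 sets the rule: "Treatment-emergent AEs will be categorised by severity". It gives the purpose in the next sentence, "All statistics will be provided to ensure that the most pertinent events (serious and severe) are not" lost among the non-serious and non-severe ones. Neither sentence mentions causality.

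SAP 5.1 runs the ER analysis on the whole Safety Set and also by age group, "gender, TEAE severity category and period of occurrence". It derives four severity categories:

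1. "Serious AEs regardless of the relationship to drug"
2. to 4. "severe and related to drug TEAEs and 3) mild and/or moderate regardless of relationship to drug, and 4) severe but not related to drug"

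The same section compares common preferred terms on ER and NNT by TEAE severity, so that the more severe "events are not 'diluted' in non-severe events". It also promises listings of fatal TEAEs, serious TEAEs and TEAEs of grade 3 or higher. SAP 5.2.2 gives an overview table with the number and percentage of subjects and the number of events by seriousness, severity and possible drug relation, each as a separate item, and repeats this by SOC and PT.

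**The concern.** Categories 1 and 3 are taken regardless of relationship. Severe events alone are cut in two by the investigator's judgement. In a randomised, double-blind, placebo-controlled safety trial, the comparison of arms is itself the evidence on causality. Sorting events by opinion before comparing the arms makes each result depend partly on how investigators attribute events.

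The practical consequence is that the simplest severity question, whether more subjects on acoziborole than on placebo have a severe TEAE, gets no pre-specified interval or test. If it is asked later with inference, it becomes post hoc under SAP section 1.

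There is a smaller gap in the definitions. SAP 3.3 treats severe and grade 3 as equivalent when imputing a missing grade, whereas the SAP 5.1 listing uses grade 3 or higher. Protocol 8.5.6 has a separate level above severe: "LIFE-THREATENING: The subject is at significant risk of life". Read literally, a non-serious CTCAE grade 4 event, such as a laboratory value, falls into none of the four categories.

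**Working it through.** **Step 1: what each place delivers for all severe TEAEs regardless of relationship.**

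| Place | Pooled over causality? | ER with 95% CI, NNT, CMH test? |
|---|---|---|
| SAP 5.1, categories 2 and 4 | No | Only for each part |
| SAP 5.1, listing of grade 3 or higher | Yes | No, listing only |
| SAP 5.2.2, overview and SOC/PT tables | Yes | No, counts and percentages |
| SAP 5.1, preferred terms by severity | Unclear | ER and NNT for preferred terms, not for all severe TEAEs as one group |

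If the SAP 5.2.2 table is shown by arm (its Overall column implies this without stating it), subtraction gives a point ER but no specified interval or test.

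**Step 2: inputs.** 900 acoziborole and 300 placebo subjects (SAP 2.4.1), and two-sided 5% tests without multiplicity adjustment (SAP 3.1). The plan's own sample-size figure reproduces: 1 − (1 − 0.002)^900 = 83.5%, as stated. The documents give no rate for severe TEAEs, so every count or rate in steps 3 to 5 is an assumption, apart from the 2% v 1% in step 5.

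**Step 3: can categories 2 and 4 be added?** Assume 9/900 v 0/300 subjects with a severe related event and 18/900 v 3/300 with a severe unrelated one. Subjects with any severe event = 9 + 18 − (subjects with both). In the acoziborole arm:

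- none with both: 27/900 = 3.0%, ER = 3.0 − 1.0 = 2.0%
- all 9 with both: 18/900 = 2.0%, ER = 2.0 − 1.0 = 1.0%

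The category results do not show the overlap, so the pooled ER cannot be derived from them.

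**Step 4: intervals for the same counts.** SAP 5.1 names the Wilson score interval. I applied its hybrid form for a difference d = p1 − p2, where l and u are the single-arm Wilson limits: lower = d − √[(p1 − l1)² + (u2 − p2)²], upper = d + √[(u1 − p1)² + (p2 − l2)²].

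| Group | Counts | ER | 95% CI |
|---|---|---|---|
| Severe, related | 9/900 v 0/300 | 1.00% | −0.35 to 1.89 |
| Severe, not related | 18/900 v 3/300 | 1.00% | −1.03 to 2.32 |
| All severe, no overlap | 27/900 v 3/300 | 2.00% | −0.11 to 3.48 |

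**Step 5: does pooling add power?** Binomial simulation, 900 v 300, unstratified Mantel-Haenszel z > 1.96 towards an acoziborole excess. Total severe rate assumed at 5% v 2% in the first three rows:

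| How the severe events are attributed | Related | Not related | Pooled |
|---|---|---|---|
| Half called related in both arms | 32% | 32% | 66% |
| 20% called related in both arms | 6% | 53% | 66% |
| Excess all called related (3.2% v 0.2%; 1.8% v 1.8%) | 97% | about 2% | 66% |
| Total 4% v 2%, half called related | 16% | 16% | 36% |

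Pooling gains when attribution is unrelated to treatment and loses when attribution is informative. At the plan's own 2% v 1% for AEs of interest (SAP 2.4.3), pooled power is only about 16%.

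**The case against.** The strongest counter-case is that little is missing.

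- A reader might infer that severe TEAEs are never pooled and their excess is not estimated anywhere. The documents do not support that. SAP 5.2.2 tabulates severity with relatedness as a separate item, and SAP 5.1 lists every grade 3 or higher event. The omission is confined to the ER analysis.
- Protocol 10.7.1 does not itself require an ER with CI for each severity level, and it names serious as well as severe events. Serious events are pooled, so part of its aim is met. This stands, but it does not explain why severe events alone are split.
- The preferred-term comparison by severity could mean plain severity. The table shells are attached separately and not visible, so an all-severe row may exist there. The SAP text does not specify one.
- A reader might point to the pivotal study's 27 treatment-emergent SAEs, "all of which were assessed as not related to acoziborole" (Protocol 1.4), and infer that the severe and related category will be nearly empty. Those are serious events, which this SAP does not split, and Protocol 8.5.6 notes that severe does not imply serious. The study was open-label in HAT patients, and Protocol 3.3 reports a timing figure for its TEAEs related to acoziborole, so investigators did make that attribution. The inference is conjecture.
- A reader might argue that the split halves the power. The third attribution in step 5 shows the reverse can happen.
- The grade 4 gap is narrow. A life-threatening event is serious under Protocol 8.5.3 and so enters category 1. What remains is the non-serious grade 4 event, which the listing captures but no ER category does.

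**Conclusion.** The concern holds in limited form. SAP 5.1 specifies no ER, 95% CI, NNT or CMH test for all severe TEAEs, and categories 2 and 4 cannot be summed to give them. This departs from Protocol 10.7.1, which categorises by severity without a causality split, and it only partly serves the SAP's own aim of keeping severe events from being diluted.

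The grounds are fidelity to the protocol and a randomised contrast that does not depend on attribution. They need no assumed rate. The size in power terms is indeterminate: for one assumed 5% v 2% total, pooled power is 66%, while the related category alone ranges from 6% to 97% according to attribution. The documents support neither a claim of lost power nor a claim that severe events go unreported. This is an inexpensive gap worth closing before unblinding, and it does not threaten the primary analysis of any TEAE.

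**What to change.** In SAP 5.1:

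- Add a category for severe TEAEs (grade 3 or higher) regardless of relationship, with ER, 95% CI, NNT, CMH test and the split by period of occurrence.
- Keep the related and not-related severe categories as a secondary breakdown of that row.
- Define severe as grade 3 or higher throughout, so that a non-serious grade 4 event is counted, and state how the levels in Protocol 8.5.6 map to it for events that CTCAE does not describe.
- Say whether the preferred-term comparison by severity uses plain severity or the listed categories.

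This needs no new data and adds one row to tables already planned. The downside is one more unadjusted comparison in a signal-detection analysis where SAP 3.1 and 5.1 already accept inflation of the type I error.
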